5.0 SUBJECT REGISTRATION

Subjects will be registered by the FHCRC/UW Study Coordinator and entered into OnCore at seattlectms.org. A complete, signed, study consent and HIPAA consent and documentation of consent are required for registration.

6.0 TREATMENT PLAN

Treatment will be administered on an outpatient basis. All study treatment will be administered at the University of Washington Medical Center or Seattle Cancer Care Alliance. Immunotherapy may be continued at the subject's local institution once the active study period is over. The active study period is defined as the concurrent nelfinavir and radiation therapy.

6.1 Nelfinavir treatment dosage and administration

Nelfinavir will be available in Investigational Drug Services (IDS) at the University of Washington and Seattle Cancer Care Alliance. When a subject is enrolled, the drug will be obtained and dispensed from IDS. It is stored at room temperature. Nelfinavir will be self-administered at a dose of 1250 mg PO BID and the patient will administer at home. This dosing is based upon the results of our phase I trial. (47) All subjects will begin taking daily oral nelfinavir 7 to 14 days prior to the start of PD1/PDL1 immune checkpoint inhibitor. Nelfinavir will be continued for a total of 11-12 weeks, depending on when Nelfinavir was initiated and when the first dose of PD1/PDL1 immune checkpoint inhibitor is. This corresponds to the duration of nelfinavir administration in the phase I trial. (47) Subjects will not receive any additional nelfinavir after the 12th week of nelfinavir, or a total of 3 bottles. The 7-14 days of nelfinavir prior to PD1/PDL1 immune checkpoint inhibitor commencement are based on the known pharmacokinetics of the drug that has shown suppression of PI-3 kinase within three days after the administration of nelfinavir (see background information). Subjects will be asked to maintain a drug diary to assess compliance with administration of nelfinavir (appendix 14.3)

6.2 Hypofractionated Radiotherapy

Hypofractionated radiotherapy typically involves fewer fractions over fewer days but each fraction involves a higher dose, compared with conventional radiation techniques. The goal of HIGRT/SBRT in this setting is to deliver appropriate tumor directed palliation while minimizing exposure of surrounding normal tissues. The dose used to treat a given tumor will be based on the location of the lesion, as the organs at risk surrounding the lesion are likely to dictate the risk of normal tissue toxicity. The study will exclude irradiation of liver metastases as an added precaution.

Patients will undergo a 3 fraction HIGRT/SBRT regimen, treatment commencing between 1st and before 3rd cycle of PD1/PDL1 immune checkpoint inhibitor. Dose and fractionation will be determined per standard clinical practice and will be dependent on the location of the treated site and adjacent organs at risk.

Either 3D-conformal radiotherapy or intensity-modulated radiotherapy (including volumetric arc radiotherapy [VMAT]) is acceptable planning techniques. Planning techniques may differ for each lesion to be treated provided that tumor motion is properly accounted for with each technique when the target is near the thorax region (i.e. lung or liver). Daily image guidance is required for this study.

6.2.1 Dose and Fractionation

Patients will undergo a 3 fraction HIGRT/SBRT regimen over 3-14 days.

The 3 fraction regimen will employ a fraction size of 8 Gy per fraction, however a dose reduction to 6 Gy is allowed if 8 Gy is not achievable due to exceeding dose constraints

Dose rate: For the purpose of this study, dose rate utilized will be that which is commissioned by the manufacturer and the medical physics group for external beam radiotherapy delivery by the University of Washington, Department of Radiation Oncology. There will be no special dose rate modifications required for this study.

6.2.2 Localization, Simulation, and Immobilization Treatment Planning / Target Volumes

All patients will be immobilized in a custom designed device in the appropriate position to isolate the index lesion. All patients will then undergo CT-based treatment planning in the custom made immobilization device. The CT scan must capture the region of interest as well as surrounding organs at risk (OAR) with sufficient margin for treatment planning. The CT scan should be obtained with a uniform slice thickness of less than or equal to 3 mm throughout. The use of IV contrast is left to the discretion of the treating physician.

All lesions with potential for respiratory motion should be evaluated by appropriate means including 4D CT scan and/or implanted fiducial marker(s). Respiratory motion management including but not limited to active-breathing control, respiratory gating, and fiducial marker tracking, will be employed for qualifying patients per standard clinical practice.

Daily image guidance will be employed for target localization with volumetric imaging (cone-beam CT).

6.2.3 Target Volumes

The gross tumor volume (GTV) is defined as all known gross disease encompassing the selected index lesion as visualized on the planning CT scan and aided by additional diagnostic imaging studies (PET/CT or MRI). The use of additional diagnostic imaging studies is dependent on the location of the index lesion and is left to the discretion of the treating physician. An internal gross tumor volume (IGTV) is defined for mobile index lesions at the discretion of the treating physician. A 4-D CT scan will be acquired in order to account for the motion of the lesion during. The IGTV will be defined as the union of the visualized index lesion on all gated CT data sets.

The clinical target volume (CTV) will equal the GTV/IGTV; there will be no margin added for microscopic extension.

The planning target volume (PTV) will be defined as per the convention for photon beam radiotherapy. A 3-dimensional margin will be created on the GTV or IGTV (if available) to allow for daily set-up variance.

6.2.4 Normal Structures

Organ at risk volume (OAR) is contoured as visualized on the planning CT or MR scan. Planning PAR is the OAR expanded for setup uncertainty or organ motion. The physician will contour the OAR. The dosimetrist will create the PAR by expanding the OAR by 2-3 mm, depending on the situation.

6.2.5 Treatment Planning

Multiple planning techniques may be employed to deliver HIGRT/SBRT to the index lesion, including static 3D coplanar and/or non-coplanar beam arrangements as well as dynamic conformal arcs or IMRT.

Three-dimensional coplanar or non-coplanar beam arrangements will be custom designed for each case to deliver highly conformal prescription dose distributions. Non-opposing, noncoplanar beams are preferable. Typically, ≥ 10 beams of radiation will be used with roughly equal weighting. Generally, more beams are used for larger lesion sizes.

For arc rotation techniques, a minimum of 340 degrees (cumulative for all beams) should be utilized. For arc rotation techniques, a minimum of 340 degrees (cumulative for all beams) should be utilized.

Critical Organ Doses: All critical organ dose-volume limits will be respected.

Planning Priorities: Every attempt will be made to successfully satisfy all of the planning goals and OAR criteria without deviation. In some circumstances, it may not be possible to meet all the ideal criteria. In these cases, spinal cord, cauda equine, sacral plexus, and brachial plexus dose constraints must be respected over PTV coverage. In the case of other OAR constraints, which are not well validated, PTV coverage and OAR constraints must be balanced per clinical practice at the discretion of the treating physician.

6.3 Toxicities and Dosing Delays

Any patient who receives treatment on this protocol will be evaluable for toxicity. Each patient will be assessed on an ongoing basis for the development of toxicity according to the study calendar (See Appendix 14.4). Toxicity will be assessed according to the NCI Common Terminology Criteria for Adverse Events (CTCAE), version 5.0. Dose adjustments should be made according to the system showing the greatest degree of toxicity.

6.3.1 Stopping rules for the study related to Grade 5 adverse events, or suspected hepatotoxicity are detailed in section 11.0 Statistical Considerations Criteria for Nelfinavir Dosing

Nelfinavir is known as a well-tolerated drug. In our phase I clinical trials [47], there were no dose-limiting or unacceptable toxicities reported. If a patient is unable to tolerate the daily dose, he/she will indicate on his/her pill diary (see Appendix 14.3) how many pills, if any, were taken that day. Efforts will be made by the study team to achieve 100% compliance by engaging in regular communication with the patient. Patients are instructed to record any symptoms they are feeling so that they can discuss it with their provider. All adverse events that are attributed as **certainly, probably, or possibly** related to nelfinavir will be recorded.

Patients will delay or discontinue treatment with Nelfinavir if they experience at least one adverse event, specified below, considered by the treating investigator to be **certainly, probably, or possibly** related to Nelfinavir treatment. Patients may continue PD1/PDL1 inhibitor Immunotherapy treatment if the criteria in 6.3.8 is not met.

The following criteria will be used to determine dosing delay, restarting doses, or discontinuing Nelfinavir treatment.

6.3.2 Criteria to delay Nelfinavir Dosing

Treatment-related Event	Action
Any > Grade 3 Adverse Event related to NFV	Delay Nelfinavir dosing

6.3.3 Criteria to resume Nelfinavir dosing

- Restart Nelfinavir dosing if/when the adverse event(s) resolve(s) to < Grade 2 severity or returns to baseline within 1 month.
 - If the adverse event has not resolved within 1 month, permanently discontinue Nelfinavir dosing
 - Restart Nelfinavir at 625mg PO BID for 1 week.
 - Monitor if adverse event re-emerges.
 - Return to 1250mg PO BID after 1 week.

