6.3.4 Criteria for permanent discontinuation of Nelfinavir

Treatment-related Event	Action
Any ≥ Grade 3 adverse event that does not improve to ≤ Grade 2 severity or return to baseline within 1 month.	Permanently discontinue Nelfinavir dosing
Any recurrence of ≥ Grade 3 adverse event that required previous Nelfinavir dosing delay	

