11.2 Analysis Plan

The primary analysis within each cohort will done on patients who receive at least one dose of nelfinavir, and anti-PD-1/PD-L1 therapy and at least one fraction of radiation. The safety analysis population will include all patients who receive at least one dose of any of the study drugs.

Binary endpoints (response, toxicity) will be summarized as proportions with associated 90% Clopper-Pearson confidence intervals. With 20 patients per cohort, binary proportions can be estimated to within 18% with 90% confidence. Any toxicity with true prevalence of at least 10% is likely to be observed (with 88% probability).

The distribution of time-to-event endpoints will be estimated using the method of Kaplan-Meier to derive estimates for median times and percentages at landmark times (e.g. 6 months). Confidence intervals for median times will be estimated using the Brookmeyer-Crowley method and for landmark times will be calculated using Greenwood's formula and based on a log-log transformation applied on the survival function.

A logistic regression model will be used to assess the association between response and factors such as smoking within each cohort. These associations will be summarized by odds ratios and associated confidence intervals and p-values. A Cox regression model will be used to assess the association between time-to-event outcomes (PFS,OS) and factors within each cohort. Similarly, these associations will be summarized by hazard ratios and associated confidence intervals and p-values.

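### As printed, Sections 6.3.3 and 6.3.4 apply different grade thresholds at the same 1-month point, so a nelfinavir-related event that has settled at Grade 2 is classified inconsistently

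*Combined protocol and SAP*

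**What the plan says.** Section 6.3 introduces the nelfinavir rules as a single working set: "The following criteria will be used to determine dosing delay, restarting doses, or discontinuing Nelfinavir treatment". It ranks none of the subsections above another.

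- **Delay (6.3.2).** Dosing is delayed for "Any > Grade 3 Adverse Event related to NFV". The sign is underlined in the supplied text, so it is read here as Grade 3 or higher.
- **Resume (6.3.3).** "Restart Nelfinavir dosing if/when the adverse event(s) resolve(s) to < Grade 2 severity or returns to baseline within 1 month". A sub-bullet adds: "If the adverse event has not resolved within 1 month, permanently discontinue Nelfinavir dosing". Restart is at a lower dose for one week. The patient is monitored for re-emergence of the event, and full dose resumes after that week.
- **Stop permanently (6.3.4).** There are two triggers. The first is a Grade 3 or higher "adverse event that does not improve to ≤ Grade 2 severity or return to baseline within 1 month". The second is recurrence, at Grade 3 or higher, of an "adverse event that required previous Nelfinavir dosing delay".

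**The concern.** Sections 6.3.3 and 6.3.4 both decide at 1 month whether nelfinavir is over for the patient, and both use the CTCAE grade reached by then or a return to baseline. They should draw the line in the same place. As printed, 6.3.3 needs the event to be below Grade 2, while 6.3.4 is satisfied with Grade 2.

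At stake is the handling of severe toxicity on the drug that this protocol adds to approved checkpoint inhibitors. If investigators rely on different subsections, one records a permanent discontinuation and another finds that the listed criterion for it is not met. Nelfinavir exposure, and the date and reason recorded for stopping, would then depend partly on which subsection was read.

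A smaller point sits beside this. Section 6.3.3 calls for a check for re-emergence during the reduced-dose week, then states the return to full dose without saying how the result of the check bears on it.

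**Working it through.** No sample size, power or error rate is involved, so the check is to apply both subsections to every state in which a patient can be 1 month after a nelfinavir-related event of Grade 3 or higher. The inputs are the delay trigger in 6.3.2, the restart and stop bullets in 6.3.3, and the two triggers in 6.3.4.

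| State at 1 month | 6.3.3 | 6.3.4 | Agree? |
|---|---|---|---|
| Grade 0 or 1 | Resolved: restart | Criterion not met | Yes |
| Back to baseline, whatever its grade | Resolved: restart | Criterion not met | Yes |
| Grade 2, baseline below Grade 2 | Not resolved: stop permanently | Criterion not met | **No** |
| Still Grade 3 or higher and above baseline | Not resolved: stop permanently | Criterion met: stop permanently | Yes |

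Only the third row conflicts. A Grade 2 baseline falls in the second row and is consistent. Before 1 month, an event at Grade 2 stays on hold under 6.3.3 and does not trigger 6.3.4, so the contradiction arises only when the month is up.

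**Can one subsection be taken to control?**

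- If 6.3.3 controls, the Grade 2 cut-off in the first trigger of 6.3.4 does no work: everyone it would stop has already been stopped under 6.3.3, together with the third-row patients.
- If 6.3.4 controls, the stop bullet in 6.3.3 is wrong for the third row. The patient is then neither permanently stopped nor eligible to restart, because the only restart rule is in 6.3.3 and needs a grade below 2, or baseline, within the month.

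Neither choice leaves both subsections meaningful, and no other section settles the case.

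**Sensitivity to the sign.** If the sign in 6.3.3 is in fact less than or equal to, the third row becomes restart under 6.3.3 and criterion not met under 6.3.4. All four rows then agree.

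**Scale per patient.** Section 6.1 gives a course of 11 to 12 weeks. One month is 4 to 4.3 weeks, that is 4/12 = 33% to 4.3/11 = 39% of the course.

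**Effect on the analysis.** Section 11.2 states: "The primary analysis within each cohort will done on patients who receive at least one dose of nelfinavir", plus at least one dose of checkpoint inhibitor and one radiation fraction. A delayed patient has already had a nelfinavir dose, so stopping or holding does not affect that condition. The cohort sizes, thresholds and power in Section 11.1 do not involve the dosing rule.

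**Re-emergence check.** Recurrence at Grade 3 or higher of the event that caused the delay is covered by the second trigger of 6.3.4. What remains unstated is whether re-emergence below Grade 3 during the reduced-dose week affects the return to full dose.

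**The case against.** The strongest objection is that the conflict may be an artefact of reading the PDF. It rests on one character. In 6.3.2 the source marks or-equal by underlining the sign, and a lost underline would turn less-than-or-equal into less-than. The underlining survives in 6.3.2 and 6.3.4, which are tables, whereas 6.3.3 is a bullet list, and nothing shows that underlining was kept outside tables. This stands as a caution. It does not dispose of the point: the signs just before and just after are marked and this one is not, and a strict sign is used elsewhere in the dosing rules (the exceptions following 6.3.8).

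The second objection is that a reader might infer that two investigators would do opposite things, with one restarting nelfinavir under 6.3.4. The documents do not support that. Section 6.3.4 lists reasons to stop. It does not say that these are the only reasons, and it gives no permission to restart. Restart is governed by 6.3.3 alone, and on its terms the third-row patient cannot restart. Read together, the only affirmative instruction for that patient is to stop. This objection stands against any claim of re-exposure. It leaves two unequal thresholds for permanent discontinuation at the same time point.

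The third objection is that the consequences are limited. Section 2.3 does not list nelfinavir discontinuation as an endpoint. The safety objectives in 2.1.2 are Grade 4 hepatotoxicity and CTCAE toxicities. Section 7.2 records all adverse events once nelfinavir has started, and the hepatotoxicity boundaries in 11.3 count events pooled over all patients. Treatment is given at two affiliated locations under one principal investigator. All of this stands.

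**Conclusion.** The rules are inconsistent as printed and need reconciling, but the defect is narrow. It concerns one state: a nelfinavir-related event of Grade 3 or higher that is at Grade 2 at 1 month, with a baseline below Grade 2. For that patient 6.3.3 requires permanent discontinuation and the 6.3.4 criterion for it is not met. The conclusion assumes that the sign in 6.3.3 is a strict less-than, as the supplied text shows.

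Two further inferences should be resisted. One is that the tolerability results become uninterpretable. Nelfinavir exposure and recorded discontinuations could be inconsistent between patients, but adverse events are captured regardless, and sample size, power and the primary analysis set do not change. The other is a count of affected patients. Section 11.3 gives a historical rate of 3% for Grade 3-4 hepatotoxicity with nelfinavir, and Section 1.3 reports no dose-limiting toxicity among 12 treated phase I patients, under a definition with exclusions. Neither gives the rate of all triggering events in this combination or the share that settles at Grade 2, so the number cannot be estimated from the documents.

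The point still merits correction because it concerns a stopping rule for severe toxicity on the added study drug.

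**What to change.** 1. Check the sign in 6.3.3 against the source page. If it means Grade 2 or lower, the conflict disappears and no change to the thresholds is needed.
2. If it is a strict less-than, amend 6.3.3 and 6.3.4 so that one grade threshold defines adequate resolution both for resuming nelfinavir and for stopping it permanently. The clinical team must choose the threshold; this review does not say which is right.
3. As a minor clarification, state in 6.3.3 how the re-emergence check bears on the return to full dose when the re-emerging event is below Grade 3, and refer to 6.3.4 for recurrence at Grade 3 or higher.

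The cost is a short text amendment, with no added visits, data or patients and no change to the statistical design.

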6.3.4 Criteria for permanent discontinuation of Nelfinavir

Treatment-related Event	Action
Any ≥ Grade 3 adverse event that does not improve to ≤ Grade 2 severity or return to baseline within 1 month.	Permanently discontinue Nelfinavir dosing
Any recurrence of ≥ Grade 3 adverse event that required previous Nelfinavir dosing delay	

6.3.5 Criteria for PD1/PDL1 inhibitor immunotherapy treatment

Patients may develop PD1/PDL1 immune checkpoint inhibitor-related toxicities that may require skipping doses or dose discontinuation. Some of these adverse events may be consistent with potentially drug-related immune-mediated phenomena; termed IRAEs.

Patients will delay or discontinue treatment with their selected PD1/PDL1 immune checkpoint inhibitor if they experience at least one adverse event, specified below, considered by the treating investigator to be **certainly, probably, or possibly** related to PD1/PDL1 immune checkpoint inhibitor treatment.

The following criteria will be used to determine dosing delay, restarting doses, or discontinuing PD1/PDL1 inhibitor immunotherapy.

6.3.6 Criteria to delay one dose of PD1/PDL1 inhibitor immunotherapy treatment

Treatment-related Event	Action
Any \geq Grade 2 non-skin related adverse event (including IRAEs) except for laboratory abnormalities	Delay PD1/PDL1 inhibitor immunotherapy dosing
Any \geq Grade 3 laboratory abnormality	
Any \geq Grade 3 skin-related adverse event (including IRAEs) regardless of causality.	

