6.3.7 Criteria to resume PD1/PDL1 inhibitor immunotherapy treatment

- Restart PD1/PDL1 inhibitor immunotherapy dosing if/when the adverse event(s) resolve(s) to \leq Grade 1 severity or returns to baseline within 3 weeks of initial dose administration
- If the adverse event has resolved (to \leq Grade 1 severity or returns to baseline), restart PD1/PDL1 inhibitor immunotherapy dosing at the next scheduled dosing time point per protocol.
- If the adverse event has not resolved in the protocol-specified dosing window (2 weeks [+/- 3 days], the next scheduled dose will be omitted.
- Patients with IRAEs who require steroid therapy with resolution to \leq Grade 1 severity must be taking no more than 7.5mg of prednisone (or the equivalent) before resuming PD1/PDL1 inhibitor immunotherapy.

6.3.8 Criteria for permanent discontinuation of PD1/PDL1 inhibitor immunotherapy for Related Adverse Events

Event	Action
Any \geq Grade 2 eye pain or reduction of visual acuity that does not respond to topical therapy and does not improve to \leq Grade 1 severity within 2 weeks of starting therapy, OR, requires systemic treatment.	Permanently discontinue PD1/PDL1 inhibitor immunotherapy
Any \geq Grade 3 bronchospasm or other hypersensitivity reaction.	

Any other \geq Grade 3 non-skin related adverse event with the exception of events listed under "Exceptions to Permanent Discontinuation"	
Any \geq Grade 4 laboratory abnormalities, except AST, ALT, or Total Bilirubin. ¹ 
 AST or ALT $> 8 \times$ ULN. Total Bilirubin $> 5 \times$ ULN. 	
Any other \geq Grade 4 adverse event.	
Any adverse event, laboratory abnormality or intercurrent illness which, in the judgment of the investigator, presents a substantial clinical risk to the patient with continued dosing.	
Any motor neurologic toxicity \geq Grade 3 regardless of causality.	
Any \geq Grade 3 treatment related sensory neurologic toxicity.	
Patients who require high dose steroids, other immune suppressants or anti-TNF drug therapy for the management of immune related adverse events should have the PD1/PDL1 inhibitor immunotherapy permanently discontinued*.	

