6.4 Immune-Related Adverse Events (irAEs): Definition, Monitoring, and Treatment

Blocking PD-L1 function may permit the emergence of auto-reactive T cells and resultant clinical autoimmunity. Rash/vitiligo, diarrhea/colitis, uveitis/episcleritis, hepatitis, and hypopituitarism are drug-related, presumptive autoimmune events, termed irAEs, noted in previous studies.

For the purposes of this study, an irAE is defined as an AE of unknown etiology associated with drug exposure and consistent with an immune phenomenon. Efforts should be made to rule out neoplastic, infectious, metabolic, toxin or other etiologic causes prior to labeling an AE an irAE.

Patients should be informed of and carefully monitored for evidence of clinically significant systemic irAE (e.g., systemic lupus erythematosus-like diseases) or organ-specific irAE (e.g., rash, colitis, uveitis, hepatitis or thyroid disease). If an irAE is noted, appropriate work-up should be performed, and steroid therapy may be considered if clinically necessary (see below).

Toxicities associated or possibly associated with PD1/PDL1 immune checkpoint inhibitor treatment should be managed according to standard medical practice. Additional tests, such as autoimmune serology or biopsies, may be used to determine a possible immunogenic etiology.

Although most irAEs observed with immunomodulatory agents have been mild and self-limiting, such events should be recognized early and treated promptly to avoid potential major complications. Discontinuation of selected PD1/PDL1 immune checkpoint inhibitor may not have an immediate therapeutic effect and, in severe cases, immune related toxicities may require acute management with topical corticosteroids, systemic corticosteroids, mycophenolate, or tumor necrosis factor alpha (TNF α) inhibitors.

The primary approach to Grade 1 to 2 irAEs is supportive and symptomatic care with continued treatment with PD1/PDL1 immune checkpoint inhibitor; for higher-grade irAEs, PD1/PDL1 immune checkpoint inhibitor should be withheld and oral and/or parenteral steroids administered. Recurrent Grade 2 irAEs may also mandate withholding PD1/PDL1 immune checkpoint inhibitor or the use of steroids.

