Assessment of the benefit risk balance should be made by the investigator, with consideration of the totality of information as it pertains to the nature of the toxicity and the degree of clinical benefit a given patient may be experiencing prior to further administration of PD1/PDL1 immune checkpoint inhibitor. The PD1/PDL1 immune checkpoint inhibitor should be permanently discontinued in patients with life threatening irAEs.

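### For a first Grade 2 non-skin, non-laboratory immune-related event such as colitis, 6.3.6 requires a checkpoint-inhibitor delay while 6.4 makes continued dosing the primary approach

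*Combined protocol and SAP*

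**What the plan says.** Two parts of the protocol tell the clinician what to do with the checkpoint inhibitor when an irAE occurs.

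**Sections 6.3.5 to 6.3.8.** Section 6.3.5 applies to events judged certainly, probably or possibly related to the inhibitor. It mentions immune-mediated events and is worded as a requirement: "The following criteria will be used to determine dosing delay, restarting doses, or discontinuing PD1/PDL1 inhibitor immunotherapy". The first row of the 6.3.6 table delays dosing for any event at or above "Grade 2 non-skin related adverse event (including IRAEs) except for laboratory abnormalities". The other two rows start at Grade 3, for laboratory abnormalities and for skin events. Under 6.3.7, once the event is at or below "Grade 1 severity or returns to baseline), restart PD1/PDL1 inhibitor immunotherapy dosing at the next scheduled dosing time point per protocol". An event that has not settled within the dosing window leads to omission of the next dose. Section 6.3.8 lists the grounds for permanent discontinuation and is followed by a short list of cases in which dosing may be resumed.

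**Section 6.4.** This section covers the definition, monitoring and treatment of irAEs. It states that "Rash/vitiligo, diarrhea/colitis, uveitis/episcleritis, hepatitis, and hypopituitarism are drug-related, presumptive autoimmune events, termed irAEs". On dosing it says: "The primary approach to Grade 1 to 2 irAEs is supportive and symptomatic care with continued treatment with PD1/PDL1 immune checkpoint inhibitor". In the same sentence it has the inhibitor withheld and steroids given at higher grades, and it then adds: "Recurrent Grade 2 irAEs may also mandate withholding PD1/PDL1 immune checkpoint inhibitor or the use of steroids". Before further dosing, "Assessment of the benefit risk balance should be made by the investigator, with consideration of the totality of information".

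**The concern.** Section 6.4 is where a clinician handling an irAE would naturally look, and its advice on continuing the inhibitor covers Grade 2 without separating colitis from rash. Section 6.3.6 does separate them, and sends Grade 2 colitis to a delay. A clinician who follows 6.4 could therefore treat a patient whose first Grade 2 colitis has not yet met the 6.3.7 restart condition.

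What is at stake is the safety of that patient, and also whether such a dose counts as a protocol deviation, which the text leaves unclear. Two features of the trial make a single clear rule more useful. Section 7.1 acknowledges that the combined effects of the inhibitor and nelfinavir have not been fully studied. Section 6.0 lets immunotherapy move to the patient's local institution after the active study period, so clinicians away from the trial site may have to apply these sections.

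**Working it through.** There is no figure to reproduce. The check sets the two rules side by side for each type of irAE, assuming that the event is at least possibly related to the inhibitor and that no 6.3.8 ground for stopping applies below Grade 3.

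| Event | 6.3.6 to 6.3.8 | 6.4 | Compatible? |
|---|---|---|---|
| Grade 1 | No delay | Continue | Yes |
| Grade 2, skin | No delay (skin row starts at Grade 3) | Continue | Yes |
| Grade 2, laboratory abnormality only | No delay (laboratory row starts at Grade 3) | Continue, if regarded as an irAE | Yes |
| Grade 2, non-skin, non-laboratory, first | Delay | Continue as primary approach | **No** |
| Grade 2, non-skin, non-laboratory, recurrent | Delay | Withholding possible | Yes, though 6.4 is the weaker |
| Grade 3 or above | Delay, or stop under 6.3.8 | Withhold; stop if life-threatening | Yes |

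One row fails. Four ways of reconciling it were tried.

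1. *Continued treatment might mean continuing after a one-dose delay.* It cannot: 6.4 sets continuing against withholding within one sentence, and its next sentence brings in withholding at Grade 2 on recurrence. A first Grade 2 event is therefore on the continuing side.
2. *6.3.6 might be meant for non-immune events.* It names irAEs in the trigger.
3. *The relatedness condition in 6.3.5 might separate the two.* Section 6.4 defines an irAE as associated with drug exposure, which ordinarily satisfies the possibly-related condition.
4. *The resumption cases after the 6.3.8 table might cover the event.* They concern local anti-tumor inflammation, admission to speed a work-up, controlled endocrinopathy, and ocular toxicity that has responded to topical treatment. Ordinary Grade 2 colitis is none of these.

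Next, does any text settle precedence? Three places might seem to:

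- The 6.3.5 sentence quoted above covers delay, restart and discontinuation. It points towards 6.3.
- Section 6.3 also says "Patients may continue PD1/PDL1 inhibitor Immunotherapy treatment if the criteria in 6.3.8 is not met". That sentence directly follows the rule for nelfinavir-related events. It concerns keeping the inhibitor going when nelfinavir is interrupted, so it does not bear on checkpoint irAEs.
- Section 6.8 removes patients from therapy when a 6.3.8 criterion applies. It deals with permanent removal, not delay.

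Only the first is relevant. It does not mention 6.4, and 6.4 does not refer back to any of 6.3.5 to 6.3.8.

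**The case against.** The strongest reply is that the protocol already shows which section sets dosing. Sections 6.3.5 to 6.3.8 are mandatory, specific and complete: they name irAEs in the introduction and in the delay trigger, and 6.3.7 has a restart condition for patients whose irAE needed steroids (no more than 7.5 mg of prednisone or equivalent). Section 6.4 is general guidance in softer terms. On ordinary principles the specific mandatory rule controls. Section 6.4 also asks for a benefit-risk assessment, and 6.3.8 lets the investigator stop for substantial clinical risk. On that view only a cross-reference is missing.

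Much of this stands. 6.3 is probably meant to govern, and a careful site would reach the right answer. It would be wrong to infer that 6.4 orders automatic dosing, because the investigator's assessment comes first. But that assessment can still end in a dose that 6.3.6 rules out, and 6.4 does not send the clinician to 6.3.6 before it is made. A cross-reference alone would also leave the 6.4 sentence saying the opposite of the rule it points to.

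A reader might also infer that the resumption cases after the 6.3.8 table waive the 6.3.6 delay for, say, a controlled Grade 2 endocrinopathy. The text does not support that: the list is about exceptions to permanent discontinuation and about resuming, and says nothing of skipping a delay.

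**Conclusion.** The point holds as an internal inconsistency that should be corrected. It affects one class of event: a first Grade 2 irAE that is neither a skin event nor a laboratory abnormality and is at least possibly related to the inhibitor. It rests on the ordinary meaning of continuing as opposed to withholding, and on the absence of a stated order of precedence.

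Two wider readings are tempting and are not supported. One is that the sections also clash at Grade 3 and above. They do not: 6.4 withholds, and 6.3.6 and 6.3.8 then determine delay or permanent discontinuation. The other is that the ambiguity weakens the efficacy results. The documents give no frequency for these events and no link between a delayed dose and response, so nothing can be said about response rate, power or the analysis population. For the same reason no number of affected patients is given.

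**What to change.** Make two changes in 6.4.

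1. State that 6.3.5 to 6.3.8, including the resumption cases listed after the 6.3.8 table, govern delay, resumption and discontinuation of the checkpoint inhibitor for all irAEs.
2. Amend the sentence on Grade 1 to 2 irAEs so that supportive care with the inhibitor continued applies only where no delay or discontinuation criterion in 6.3.6 or 6.3.8 is met.

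Keep the discretion to withhold or give steroids for recurrent Grade 2 irAEs. Do not write a separate category of laboratory irAEs into 6.4. The protocol defines no such class, and text directing continued dosing for it could be read as covering Grade 2 immune hepatitis, when 11.3 names hepatotoxicity as a key concern. Naming the resumption cases in the first change prevents a new conflict with them, since a controlled endocrinopathy may resume on terms other than those in 6.3.7.

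The cost is a wording amendment: one added statement and one revised sentence. No threshold in 6.3, study procedure or design figure changes.
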